HOME-BASED RESISTANCE TRAINING IN ENDOMETRIAL CANCER SURVIVORS

Feasibility and acceptability of a telehealth-based resistance training intervention for endometrial cancer survivors

**Principal Investigator:
[name].
University of Wisconsin - Madison**

This document is confidential.

No part of it may be transmitted, reproduced, published, or used by other persons without prior written authorization from the Sponsor or Principal Investigator.

PROTOCOL VERSION and AMENDMENTS

[figure not shown]
Protocol Version	Date	Change Initiated (Initials)	Brief description of protocol modification/actions requested, if any
Version 1.0	2/5/2018	[name]	Preliminary draft
Version 1.1	2/7/2018	[name]	Updated for review by PRMC at UWCCC
Version 1.2	2/13/2018	[name]	Updated post meeting [name]
Version 1.3	3/9/2018	[name]	Updated again for review by PRMC
Version 1.4	4/2/2018	[name]	Updated post-review of PRMC
Version 1.5	4/19/2018	[name]	Update: mental health questions, repeated measures and qualitative measures added
Version 1.6	7/5/2018	[name]	Updated informed consent as separate document
Version 1.7	7/14/2018	[name]	Updated a new, streamlined checklist in the appendix
Version 1.8	08/24/2018	[name]	Revised after IRB pre-review
Version 1.9	08/30/2018	[name]	Revised after second IRB pre-review
Version 1.10	09/26/2018	[name]	Updated post PRMC re-review
Version 1.11	10/04/2018	[name]	Updated after PRMC, QA and Compliance manager review at the UWCCC.
Version 1.12	11/24/2018	[name]	Updated the participant compensation information due to oversight in previous versions.
Version 2.1	3/19/2019	[name]	R03 awarded: updating accrual goals, length of intervention, recruitment strategies

1 Study Summary

Title	Feasibility and acceptability of a telehealth-based resistance training intervention for endometrial cancer survivors
Short Title and Precise	Home-based resistance training in ECS
Protocol Number	UW18013
Methodology	Randomized, two arms including a wait list control
Study Duration	One year
Study Center(s)	UW-Madison
Objectives	Determine adherence rates to prescribed exercises, quantify changes in lean body tissue and blood biomarkers, and functional changes in performance
Number of Subjects	40
Diagnosis	Endometrial cancer
Main Inclusion Criteria	Diagnosis of Type I, stage I-IIIc endometrial cancer, with completion of primary treatment
Main Exclusion Criteria	Absolute contraindications to exercise, failure on pre-MVPA screening
Study Product, Dose, Route, Regimen	Home-based, full-body resistance training exercises of 2-3 sets of 8-10 reps two days a week for 10 weeks, with a five week follow up period
Statistical Methodology	Paired comparisons to assess pre-post differences within groups, as well as between groups pre and post

Schematic of Study Design

Flow diagram or study calendar (e.g., randomized controlled trial)

Contents

HOME-BASED RESISTANCE TRAINING IN ENDOMETRIAL CANCER SURVIVORS	1
1 Study Summary.....	2
2 Key Roles.....	5
2.1 Background and Rationale	5
2.2 Aims and Hypotheses	6
2.3 Potential Risk and Benefits to Subjects.....	7
3 Study Aims.....	8
4 Study Design and Endpoints	8
5 Study Infrastructure.....	8
6 Study Subjects – Enrollment and Withdrawal.....	8
6.1 Subject Population	9
6.4 Subject Screening for Recruitment.....	9
7.5 Vulnerable Populations	10
7.5.1 Subject Capacity	10
7.6 Informed Consent.....	10
7.7 Early Withdrawal of Subjects.....	11
8 Study Procedures	12
8.1 Measures.....	13
8.2 Video calls	14
8.3 Labs.....	15
8.4 Established Standard of Care:	15
8.5 Study Visits.....	15
9 Study Analysis	16
9.1 Sample Size Determination	16
9.2 Statistical Methods	16
9.3 Subject Population(s) for Analysis.....	16
9.4 Planned Interim Analysis:.....	17
10 Data Collection, Handling and Record Keeping	17
10.1 Data Confidentiality	17
10.2 Data Capture	17
10.3 Records Retention.....	18
10.4 Data and Safety Monitoring	18
11 Assessment of Safety	19
12 Study Finances	19
12.30 Funding Source	19
12.31 Conflict of Interest.....	19
12.32 Subject Stipends or Payments.....	19
13 Publication Plan	19
14 Protocol implementation timeline and contingency plans.....	19

2 Key Roles

Following is a list of all personnel in key roles:

Principal Investigator: PI

[name], Assistant Professor of Kinesiology

University of Wisconsin-Madison

[name]

[name]

[contact]

[contact]

Co-Investigator / Medical monitor

[name], Assistant Professor

University of Wisconsin-Madison

[name]

[name]

[name]

[contact]

Biostatistician

[name], Professor of Population Health Sciences/Biostatistics

University of Wisconsin-Madison

[name]

[name]

[name]

Project Coordinator

[name], MS, Research Fellow

University of Wisconsin-Madison

[name]

[name]

[contact]

[contact]

Introduction

This document is a protocol for a human research study. This study is to be conducted according to applicable government regulations and Institutional research policies and procedures, and State Law.

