8.5 Study Visits

8.4.1 Screening/Baseline:

Baseline. At this visit, the study coordinator will explain the study and obtain written informed consent. Physical measurements (anthropometrics, blood sample, DXA scan, functional fitness testing) will be completed. The study coordinator will instruct the participant on how to properly wear the accelerometer (to be returned via pre-paid mailer), complete a 7-day PA log, and complete the online questionnaires.

Randomization. After all baseline measures have been completed and checked, the participant will be randomized with 1:1 probability to the intervention or wait-list control group. A blocked randomization scheme will ensure equal allocation of participants to each group. Participants will be notified of their group assignment by phone; those in the intervention group

Table 4. Acceptable Window for Study Visits (including weekends)

Visit	Window	Activities
Randomization	+/- 5 days	Allocate to group
Instructional visit	+/- 2 weeks	Teach exercises, learn how to interface with software, how to log exercises
Final visit	+ /- 2 weeks	Collect final measures

8.4.3 Unscheduled:

- Pain or concerns that need to be addressed in person
- Adverse event follow ups with PCP

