8.4.4 Final Study Visit

Final Visit. All participants will return for follow-up assessments at 10 weeks. In advance, the participant will be mailed an accelerometer and 7-day PA log and will receive a link to complete the online questionnaires. Physical measures (anthropometrics, blood sample, DXA scan, functional fitness testing) will be completed. Those women in the wait-list control group will receive their introductory intervention session at this visit.

9 Study Analysis

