9.2 Statistical Methods

As this is the first investigation in this population to look at this resistance training, both in terms of adherence rates as well as objective and functional changes in performance, there are no published effect sizes to anticipate at this time; therefore, we have a feasibility/descriptive focus as opposed to a hypothesis-testing focus. In addition to quantitative analysis, we plan to conduct qualitative analyses from participant feedback surveys to assess barriers to participation and to improve future interventions and to increase adherence rates.

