9.3 Subject Population(s) for Analysis

The populations for this investigation include:

- All-randomized population: Any subject randomized into the study, regardless of whether they received study agent
- All-treated population: Any subject randomized into the study that received at least the instructional visit of the intervention
- Protocol-compliant population: Any subject who was randomized, was allocated to the exercise group and provided at least one set of data elements required by the protocol.

9.3.1 Describe the types of analysis:

- **Primary Analysis:** The primary objective includes measuring the percentage of completed sessions compared to prescribed, and a one-sample t-test will be conducted to determine if that proportion, across participants, is >90%. A one-sample t-test will be done to determine if retention is >90%.

- **Secondary Analyses:** The secondary analyses includes measuring the objective and functional changes from pre to post intervention as well as differences between groups. Paired ANOVAs and descriptive statistics will be used to analyze functional and objective data, as well as participant feedback data, including satisfaction with each component of the intervention.
- **Exploratory, longitudinal analyses:** Content analysis will be done on the qualitative interviews to examine barriers to physical activity, as well as satisfaction with the intervention, and identification of themes to improve the intervention. Although formal hypothesis testing is not part of our specific aims, we will conduct longitudinal analyses of the data we collect to estimate potential magnitude of expected changes, as well as longitudinal analysis of the repeated measures.
- **Safety Analysis:** The safety analysis includes simple descriptive analysis about the number of adverse events over the course of the intervention between groups and across sites.

9.4 Planned Interim Analysis:

There are no planned interim analyses for this investigation.

10 Data Collection, Handling and Record Keeping

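### The between-arm estimate for the secondary physical outcomes is worded as paired and never named; a baseline-adjusted week-10 difference would be clearer and usually slightly more precise

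*Combined protocol and SAP*

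**What the plan says.** The Statistical Methodology row of the synopsis (section 1) names one method for both kinds of comparison: "Paired comparisons to assess pre-post differences within groups, as well as between groups pre and post".

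Section 9.3.1 sets two targets for the secondary analyses, "measuring the objective and functional changes from pre to post intervention as well as differences between groups". The next sentence gives the method: "Paired ANOVAs and descriptive statistics will be used to analyze functional and objective data". The exploratory analyses are then meant "to estimate potential magnitude of expected changes", again without a model. No section names an arm contrast, an arm-by-time term or a baseline covariate.

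The data for an adjusted contrast are already planned. At the baseline visit (8.4.1, under 8.5), "Physical measurements (anthropometrics, blood sample, DXA scan, functional fitness testing) will be completed". Allocation follows: "After all baseline measures have been completed and checked, the participant will be randomized with 1:1 probability". The scheme is blocked, with no matching of individuals. At the 10-week visit that all participants attend (8.4.4), "Physical measures (anthropometrics, blood sample, DXA scan, functional fitness testing) will be completed". The wait-list paragraph of section 8 confirms that the control arm has the same measures.

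Section 9.2 sets the overall frame: "we have a feasibility/descriptive focus as opposed to a hypothesis-testing focus".

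**The concern.** A paired comparison needs a link between the two values compared. Each woman's baseline and week-10 values are linked, but a woman in the exercise arm has no partner in the wait-list arm. The synopsis nevertheless puts the between-group comparison under the paired heading, and 9.3.1 does not say what the between-arm estimate is.

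An analyst could therefore choose among several estimates after seeing the data: the arm difference in change, the arm difference at week 10 alone, or a baseline-adjusted difference. The synopsis wording also covers a comparison of the arms at baseline. After randomisation that comparison reflects chance only and says nothing about the intervention.

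What is at stake is modest: how reproducible and how precise the between-arm estimates are that this pilot intends to report and that may inform a larger study.

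**Working it through.** **No figure to reproduce.** Section 9.1 chooses N = 40 for feasibility. The documents give no effect size, SD, pre-post correlation, alpha or power for these outcomes.

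**Inputs from the documents.** N = 40 at 1:1 is 20 per arm. Section 6.4.3 expects about 5% loss, so n = 19 per arm.

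**Assumptions.** Two-sided 95% intervals, results in units of the outcome SD, the same SD at baseline and week 10, and pre-post correlation r from 0.5 to 0.9.

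**Formulas for the SE of the arm difference**
- Week-10 values only: sqrt(2/n)
- Change: sqrt(2(1 − r) × 2/n)
- ANCOVA: sqrt((1 − r²) × 2/n)

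The ratio ANCOVA/change is sqrt((1 + r)/2), which is 0.866, 0.922 and 0.975 at r = 0.5, 0.7 and 0.9. That is before any small-sample cost.

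**CI half-widths at n = 19.** The t quantile is 2.028 (36 df) without adjustment and 2.030 (35 df) for ANCOVA. ANCOVA also carries a factor for chance baseline imbalance, sqrt(1 + 1/(2n − 4)) = sqrt(1 + 1/34) = 1.0146.

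| r | Change | ANCOVA | ANCOVA narrower by |
|---|---|---|---|
| 0.5 | 2.028 × 0.324 = 0.658 | 2.030 × 1.0146 × 0.281 = 0.579 | 12.0% |
| 0.7 | 2.028 × 0.251 = 0.510 | 2.030 × 1.0146 × 0.232 = 0.477 | 6.4% |
| 0.9 | 2.028 × 0.145 = 0.294 | 2.030 × 1.0146 × 0.141 = 0.291 | 1.0% |

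**Where the gain runs out.** The widths are equal when sqrt((1 + r)/2) = 2.028/(2.030 × 1.0146) = 0.985, so r is about 0.94. At r = 0.95 the ANCOVA interval is 0.3% wider, and at r = 0.98 about 1% wider.

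**Unequal SDs.** Let k = SD(final)/SD(baseline). The SE ratio becomes sqrt((1 − r²)/(1 + 1/k² − 2r/k)). With the same small-sample costs at n = 19:
- k = 0.8: 23.2%, 19.5% and 20.8% narrower at r = 0.5, 0.7 and 0.9
- k = 1.25: 4.0% narrower, 0.6% wider and 1.0% narrower

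**How far the two point estimates can differ.** With equal SDs, ANCOVA minus change is about (1 − r) times the baseline arm difference. At 20 per arm its SD is (1 − r) × sqrt(2/20), or 0.158, 0.095 and 0.032 outcome SD at r = 0.5, 0.7 and 0.9.

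**Week-10 values only, n = 19.** The half-width is 2.028 × sqrt(2/19) = 0.658. Against this, ANCOVA at 0.579, 0.477 and 0.291 is 12%, 28% and 56% narrower.

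**The case against.** The best defence is that 9.3.1 contains no error. It lists two targets in one sentence and a method in the next, and it does not expressly assign the paired method to the arm contrast. A paired ANOVA is most naturally a repeated-measures ANOVA, in which pairing describes the time factor within each woman and the group-by-time term is the arm difference in change. That contrast is unbiased under randomisation, as is ANCOVA, so the choice between them is one of precision. This stands. A reader might infer that the plan will run a paired test across independent arms, or that its estimates will be biased. The documents do not support either.

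The second defence is scale. The gain rests on a correlation that the documents do not give, it shrinks to 1% at r = 0.9, and it turns into a small loss above about 0.94. The study disclaims hypothesis testing, and no sample-size calculation rests on these contrasts. This stands too: the change is cheap, but it is not a gain in every case.

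Neither defence supplies the missing contrast. Even on the favourable reading the plan does not name it, and the synopsis still admits visit-by-visit comparisons, including one at baseline.

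**Conclusion.** The point holds as a clarity and efficiency improvement worth considering. The between-arm estimate for the physical outcomes is valid on the natural reading, but it is unnamed, loosely labelled as paired, and usually a little less precise than a baseline-adjusted one. With equal SDs and 19 per arm, the CI is about 12%, 6% and 1% narrower at r = 0.5, 0.7 and 0.9. Allowing the SD ratio to run from 0.8 to 1.25 over the same correlations, the change runs from 23% narrower to 0.6% wider.

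A reader might be drawn to the 12-56% gain over a week-10-only comparison. That is the gain only if the visits are compared separately, which the synopsis wording permits but which is not the natural reading. It should not be quoted as the cost of the plan.

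Nor does the point reach the main conclusions. The primary adherence endpoint, Aims 1-3 and N = 40 are unaffected.

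**What to change.** In the synopsis and 9.3.1, keep paired methods for within-arm change, remove the word for the between-arm part, and add text such as:

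> For body composition, functional fitness, anthropometrics and blood biomarkers, the between-arm estimate is the week-10 difference adjusted for the pre-randomisation baseline value (ANCOVA: week-10 value on arm and baseline value). It includes all randomised women with data, in the arm assigned, and is reported as a descriptive estimate with its 95% CI, the SD and the pre-post correlation. Within-arm changes are descriptive. Baseline differences between arms are not tested.

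The cost is wording in two places and one degree of freedom per model, with a CI up to about 1% wider at r = 0.98. No extra data, visits or participants are needed, because both measurements are already planned in both arms. Reporting the SD and correlation also gives a later trial planning inputs that this protocol lacks.

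The timing of the first accelerometer wear, the order of the baseline questionnaires and the week-5 measures are separate matters and are not part of this change.

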2.1 Background and Rationale

Endometrial cancer survivors have an extremely high prevalence of inactivity and obesity. The US has a large and rapidly growing population of 760,000 endometrial cancer survivors, which will increase 55% by 2030.^{1,2} Despite a generally favorable 81% 5-year survival rate, patients remain at increased risk for cardiovascular disease, diabetes, and other cancers.³ A key risk factor for endometrial cancer is unopposed estrogen, which is linked to inactivity and obesity.^{4,5} Indeed, up to 90% of Type 1 endometrial cancer patients are obese.⁶ Inactivity and obesity are associated with poorer outcomes among survivors. In the NIH-AARP Diet and Health Study, endometrial cancer survivors who were physically active had a lower all-cause 5-year mortality rate and lower BMI was associated with lower risk of both overall and disease-specific mortality.⁷

There is a critical need for data about the feasibility and benefits of strength training in this population. Other interventions have demonstrated that walking and aerobic exercise are safe and feasible in endometrial cancer patients.⁸⁻¹¹ However few published studies have examined strength training in endometrial cancer survivors, and these have done so only in combination with aerobic PA intervention (and often also dietary change) in the context of a larger multi-component intervention.^{12, 13} Therefore the specific contribution of strength training remains unknown. This is important because aerobic exercise leads to improvements in the cardiovascular system, whereas resistance training has specific effects at the musculoskeletal level in addition to systematic cardiovascular benefits.¹⁴ Strength training increases muscle mass, which is critically important given the high prevalence of sarcopenic obesity among middle-aged and older women.¹⁵ It is also highly effective for functional improvements such as increased strength and balance.^{16, 17} Indeed, in other cancer survivor groups, strength training is more effective than aerobic exercise for improving functional status.¹⁴ Another benefit of strength training is that it is a realistic health promotion option given poor long-term efficacy of weight loss interventions.¹⁸ Unfortunately, without intervention, strength training has a relatively high barrier to participation among women, due to factors such as lack of knowledge and difficulty finding time to travel to a gym.¹⁹

Previous strength training interventions not optimized for rural populations. Rural areas are often underserved in terms of medical access/use and educational and economic opportunities.^{20, 21} Consequently, rural populations are diagnosed at later stages of cancer²² and have higher rates of cancer mortality.²³ Unfortunately, previous strength training research in cancer populations have mainly used supervised sessions with a personal trainer at a gym, an approach that is not feasible in many rural settings.

Overview of proposed research. To address these gaps, we propose a 2-arm pilot trial of a home-based strength training intervention (vs. waitlist control) among 40 endometrial cancer survivors. The intervention will consist of (a) an initial in-person instructional session; (b) instructional materials and resistance training equipment (e.g., resistance bands) and (c) support and feedback provided via video coaching sessions. The purpose of a pilot trial is not to conduct hypothesis testing, but rather to field-test the logistical components of the study to incorporate into a larger, future study design.²⁴ With small samples, the true effect size is more likely to be under or overestimated, therefore hypothesis testing is not valid.²⁵ Our aims are designed accordingly.

2.2 Aims and Hypotheses

The proposed trial will determine the feasibility of an at-home resistance training protocol and measurements of exercise logging, functional fitness testing, DXA, dried blood spots and questionnaire measures. Participants will be assigned either to the resistance training program (i.e., initial in-person instructional session, telephone coaching, and self-monitoring) or to a comparison arm (wait-list control).

- **Aim 1:** To determine the feasibility of recruiting and retaining endometrial cancer survivors to a home-based resistance training 2 sessions per week of 20-40 minutes of exercise. *We hypothesize that we will meet the accrual goal and maintain >90% retention.*
- **Aim 2:** To determine participant satisfaction with each component of the intervention and identify opportunities for refinement of the intervention prior to testing in a larger study. *We hypothesize that the participants will adhere to 90% of the prescribed exercise sessions and that overall satisfaction will be high.*
- **Aim 3:** To establish that functional and objective assessments are feasible and well-tolerated in enrolled participants, as assessed using the functional fitness test (FFT) battery, dual-energy x-ray absorptiometry (DXA), finger-pricks for dried blood spots and patient-reported outcomes. *We hypothesize that these assessments will be well tolerated, as measured by the percent of participants who complete all measures and data from participant feedback questionnaires.*

2.3 Potential Risk and Benefits to Subjects

2.3.1 Known Potential Risks

Potential risks of participating in this study include musculoskeletal soreness and a possible loss of confidentiality, either through the breach of non-identifiable data collected online, or through the breach of secure study databases or physical files.

Potential Benefits of the Proposed Research to Human Subjects and Others: Findings from the proposed study will contribute to the scientific knowledge of the feasibility of resistance training interventions in endometrial cancer survivors. Additionally, the knowledge gained will contribute to the scientific knowledge aimed at understanding the potential therapeutic benefits of resistance training exercise for endometrial cancer survivors. The risks of our study procedures are low and therefore are seen as justifiable in regards to the knowledge to be gained.

Importance of Knowledge to be gained: Increasing physical activity after a cancer diagnosis is an important area of researching, and finding feasible interventions for endometrial cancer survivors are key to sustainable lifestyle changes. This research will take the first step that will provide valuable information and serve as a scaffolding for the continued design and development of future interventions.

